6.1.2 Durability of the device

- The absence of revisions/removal due to pain and/or loosening.
- Radiological integrity. The integrity of the implant / bone interfaces will be assessed. The occurrence of radiolucent lines / radiolucency being defined as a clearing or radiolucent line not exceeding 2 mm in width at the bone / prosthesis.
- Progressive radiolucency being defined as radiolucencies which increase no more than 2mm in two or more zones in the femoral or tibial implants.
 - Anterior-Posterior (AP) view
 - Skyline (Merchant View) at 30 degree Knee Flexion
 - Lateral View

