1.3. Beads

To evaluate the motion of the polyethylene bearing and micromotion of the prosthesis, at least three well-scattered tantalum balls (∅ 1.0 mm) have to be inserted into the tibia and femoral bone. To this end a special designed Ta-marker insertion device will be used according to instructions of the manufacturer (Halifax Biomedical, NS, Canada). The beads are not part of the Knee system itself. The bead inserter

device will be loaned to the hospital by Stryker for the duration of the clinical study (covered in study contract).

2. Objectives of the Clinical Investigation

- The primary objective is the assessment of the in vivo wear of the two randomized polyethylene inlay types N2Vac and X3 by means of Roentgen Stereophotogrammetry. It is expected that the X3 group will show significantly less wear after 5 years compared to the conventional N2Vac polyethylene group.
- The secondary objective is the assessment of prosthetic migration results after two years of the Triathlon CS Peri-Apatite coated tibial and femoral components by means of Roentgen Stereophotogrammetry. It is expected that due to the superior wear qualities of X3 polyethylene this group will show significantly less migration of the prosthesis' components after two-years compared to the components in the N2Vac group.
- The third objective will be the prediction of the long-term survival of the Triathlon CS Peri-Apatite coated tibial and femoral components based on the two-year migration patterns combined with clinical factors and radiographic aspects. In order to identify other clinical parameters besides wear influencing the fixation of the prosthesis components, clinical scores and radiographic aspects will be correlated with the RSA outcome. Subsequently, a long-term prediction can be for the Triathlon CS Peri-Apatite coated tibial and femoral components.

3. Design of the Clinical Investigation

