6.1.3 Patient success or failure

Each patient from the two groups must meet the following criteria at the two-year (± 2 months) evaluation in order to be considered as “success”:

Patient Success - defined by the following requirements at the two-year follow-up interval:

- A Knee Score of ≥ 80, and
- No component revisions or removals (femoral, bearing, tibial or patella), and
- No pending component revisions or removals (femoral, bearing, tibial or patella) and
- Absence of Osteolysis in any component (femoral, bearing, tibial or patella) and
- No migration / subsidence of >3mm or >3° in any component (femoral, bearing, tibial or patella)

A patient who meets any of the following criteria at the two-year (\pm 2 months) evaluation will be considered as “failure”:

Patient Failure – defined by the following requirements at the two-year follow-up interval:

- A Knee Score of < 80 , or
- Revisions or removals of any component (femoral, bearing, tibial or patella), or
- Pending revisions or removals of any component (femoral, bearing, tibial or patella), or
- Presence of Osteolysis in any component (femoral, bearing, tibial or patella), or
- Migration / subsidence of 3 mm or $>3^\circ$ in any component (femoral, bearing, tibial or patella).

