6.3. The RSA Procedures

The fixation and stabilization of the tibia components will be assessed using RSA. During the surgical procedure at least three well-scattered tantalum markers are installed (\varnothing 1.0 mm) into the bone around

the tibial component to obtain skeletal landmarks. The tantalum markers are locked inside a rotating cartridge inside a specially designed insertion instrument (Halifax Biomedical, NS, Canada).

At the routine control visits (discharge day, 6 weeks, 3, 6, 12, 24 months and 5 years), the radiographs will be taken and the physical evaluation will be performed.

The RSA data of the prostheses components will be compared in terms of subsidence, linear, and rotational movements and wear. If the prosthesis is stable and fixed the differences will be zero.

The RSA set-up consist of two synchronized roentgen tubes positioned approximately 1.5 meter above two roentgen cassettes (35*43 cm) at a 20° angle to the vertical. Both roentgen tubes simultaneously expose the roentgen film. A carbon fiber calibration box (Medis specials b.v., Leiden, The Netherlands) is used to calibrate the experimental set-up (loaned by Stryker to the hospital for the duration of the study, covered in study contract).

The RSA X-rays of the discharge day (4-7 days postoperative) is used as baseline. Since the tantalum balls are fixed in the bone around the tibial implant, the position of the implant relative to the bone can be calculated. Taking these bone markers as reference points, the spatial translations and rotations of the tibial component during follow-up can be calculated (Kaptein et al., 2006; Valstar et al. 2005). The bone markers need to be well fixated in the bone. Bone markers are defined unstable when they move more than 0.3 mm with respect to the other bone markers. Unstable markers will be excluded from analysis (Garling et al. 2005b).

For the analysis of wear the same principle can be used. Taking the tibial component as a reference, the spatial translations and rotations of the femoral component during follow-up can be calculated. The relative change in proximal – distal direction of the femur with respect to the tibia will be denoted as polyethylene wear.

7. Adverse Events

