8.2. Potential Risk

The study involves the routine assessment of a knee arthroplasty procedure. The device under study has been cleared for marketing and has the CE mark. It will be used according to its labelling. Assessment involves questionnaires, patient and physician assessments, and RSA-radiographs. The effective radiation dose per RSA-radiograph is 3 μ Sv (Teeuwisse *et al.*, 1998). The additional annual radiation dose is negligible if the natural annual exposure of 2 mSv is considered and will do the patient no harm (Blake *et al.*, 1996). The International Commission on Radiological Protection categorizes the corresponding level of risk qualitative due to radiation as 'trivial' with a quantitative risk of about one in a million or less. The required level of benefit should be related to 'only increase knowledge'. (http://ec.europa.eu/energy/nuclear/radioprotection/publication/099_en.htm)

The information collected will be kept confidential.

Serious complications may be associated with any total joint replacement surgery. These complications include, but are not limited to: infection, genitourinary disorders, gastrointestinal disorders, vascular disorders, including thrombus, bronchopulmonary disorders, including emboli, myocardial infarction and death.

With all implanted devices, asymptomatic, localized progressive bone resorption (osteolysis) may occur around the prosthetic components as a consequence of foreign-body reaction to the particulate matter of metal or polyethylene (X3, UHMWPE). Particulate is generated by interaction between components as well as adhesion, abrasion, and fatigue. Secondly, particulates can also be generated by third body wear. Osteolysis can lead to future complications, including loosening, necessitating the removal and replacement of prosthetic components.

Early and late loosening of total knee components can occur. Early biomechanical loosening may result from inadequate initial fixation, latent infection, premature loading of the prosthesis or trauma. Late loosening may result from trauma, infection, biological complications including osteolysis or mechanical problems, with the subsequent possibility of bone erosion and/or pain.

Peripheral neuropathies, circulatory compromise and heterotopic bone formation may occur.

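### Section 6.1.2 bounds radiolucency and progressive radiolucency only from above at 2 mm, so the worst lines fall outside the definitions and the adverse state is never defined

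*Combined protocol and SAP*

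**What the plan says.** Section 6.1.2 lists what will be taken as evidence of durability. The first item is a favourable state: "The absence of revisions/removal due to pain and/or loosening". The second, radiological integrity, gives a width: "The occurrence of radiolucent lines / radiolucency being defined as a clearing or radiolucent line not exceeding 2 mm in width". The third concerns change over time: "Progressive radiolucency being defined as radiolucencies which increase no more than 2mm in two or more zones", for the femoral or tibial implants.

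Three other places bear on the point.

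- Section 6.1.3 makes osteolysis a failure criterion, with no width or growth figure.
- Section 8.2 describes osteolysis in words only: "asymptomatic, localized progressive bone resorption (osteolysis) may occur around the prosthetic components".
- Section 2, under the third objective, says that "clinical scores and radiographic aspects will be correlated with the RSA outcome", without listing which radiographic aspects are meant.

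Section 9.1 assigns chi-square or Fisher tests to categorical outcomes in general and gives no cut-off for radiolucency.

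**The concern.** A definition of an adverse radiographic finding would be expected to catch the larger changes. These two catch the smaller ones and stop at 2 mm. A reader who applies the words as they stand would label slight growth *progressive* and have no label for rapid growth. A wide line would not qualify as a radiolucency at all.

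At stake is how the radiolucency items are classified and compared between the N2Vac and X3 groups. The blinding in section 5.3 guards against bias by arm, but it does not tell a reader which category a film belongs in. A chi-square or Fisher test needs categories that cover every film. If radiolucency is one of the aspects correlated with migration under the third objective, the same gap carries into that analysis.

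**Working it through.** The plan gives no figure to reproduce and no sample-size or power quantity is involved. The check reads the two definitions as inequalities and then looks for any other text that covers what they leave out.

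**Inputs, both from 6.1.2.** Let w be the width of a line on the follow-up film and g its increase.

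- Radiolucency: w ≤ 2 mm.
- Progressive radiolucency: 0 < g ≤ 2 mm, in two or more zones. The lower bound of 0 follows from the word *increase*.

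**One consequence by arithmetic.** A line cannot start narrower than 0 mm, so w ≥ g. If g > 2 mm, then w > 2 mm. Growth above 2 mm therefore fails both definitions.

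**Illustrative cases, chosen to show the logic (not patient data).**

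| Case | Literal definitions | Read as acceptance limits |
|---|---|---|
| g = 0.5 mm in two zones, w within 2 mm | Radiolucency, and progressive | Acceptable, yet labelled progressive |
| g = 3 mm in two zones (so w ≥ 3 mm) | Neither | Over both limits; no named category |
| w = 3 mm, no growth | Neither | Over the width limit; no named category |
| g = 0.5 mm in one zone only, w within 2 mm | Radiolucency; its growth has no category | Width acceptable; growth not addressed |

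One qualification is needed. A line that goes from 1.0 to 2.5 mm in two zones has g = 2.5 − 1.0 = 1.5 mm. It is too wide for the first definition but could still be called progressive under the second, if the second is not limited to lines that remain within 2 mm. So it would be too much to say that every line wider than 2 mm is without a label. What always lacks one is growth above 2 mm.

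**Does other text close the gap?**

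- Osteolysis in 6.1.3 has no width at which a line becomes osteolysis, and no link to 2 mm. The wording in 8.2 is qualitative.
- The 3 mm and 3° limits in 6.1.3 concern component migration.
- Section 9.1 has no radiolucency rule.
- The reference list includes a Knee Society radiographic evaluation and scoring system for total knee arthroplasty, but 6.1.2 does not invoke it and states its own definitions.

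None of these classifies a lucency above either limit.

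**The case against.** The best defence is that the two bullets state what a sound interface may show. Section 6.1.1 lists favourable outcomes (pain relief, restored function), and 6.1.2 opens with freedom from revision. In that company, limits of at most 2 mm read naturally as acceptance limits, and anything larger fails by complement. The success criterion in 6.1.3, "No migration / subsidence of >3mm or >3° in any component (femoral, bearing, tibial or patella", has the same form: it bounds an acceptable state from above. A reader might infer that the plan words its other limits the opposite way and that 6.1.2 is therefore a plain inversion. The documents do not support that. The clear example of an adverse threshold is the RSA quality rule, "Bone markers are defined unstable when they move more than 0.3 mm with respect to the other bone markers", which concerns markers and not patient outcome.

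This makes the acceptance reading plausible but does not repair the text. Both bullets are worded as definitions and neither is labelled as a limit of acceptability. On that reading *progressive* names the acceptable state, although 8.2 uses the word for an adverse process, and the adverse state still has no definition.

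Two further objections stand in part. The case report form is not in the supplied text and may carry coding rules, so actual disagreement between readers cannot be shown. Radiolucency is also not among the parameters for which 9.1 promises confidence intervals, so no planned headline result is shown to change.

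**Conclusion.** The wording is defective on either reading. Literally, the largest growth and the widest stable lines fall outside the durability definitions. As acceptance limits, the adverse side is left to inference and the label is misleading. This should be corrected, but it is a limited matter.

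Its reach is the radiolucency items of a non-primary durability parameter. It extends to the third objective only on the assumption that radiolucency is among the unspecified radiographic aspects. The primary wear endpoint, the sample size and the 6.1.3 success and failure lists do not use radiolucency and are unaffected. The documents give no lucency frequencies, so the number of knees concerned cannot be stated.

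A reader might also infer that wide lines will be missed or lost from the data. That does not follow: 6.1.2 says the interfaces will be assessed and section 6 schedules radiographs through 5 years. What is missing is the classification of such lines.

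**What to change.** Reword the two bullets together so that a lucency above the stated 2 mm width limit or the stated 2 mm growth limit is explicitly counted on the adverse side. Label each bullet as an event definition or an acceptance limit, consistently with that. State how growth up to 2 mm is classified, and how growth in a single zone is classified. The sponsor must reconcile the wording; no threshold is proposed here.

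The cost is about two sentences in 6.1.2. If the case report form already records width by zone (an assumption), no new data are needed. If it does not, the form would need aligning, and any films already read would have to be re-read for width.

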6.1.3 Patient success or failure

Each patient from the two groups must meet the following criteria at the two-year (± 2 months) evaluation in order to be considered as “success”:

Patient Success - defined by the following requirements at the two-year follow-up interval:

- A Knee Score of ≥ 80, and
- No component revisions or removals (femoral, bearing, tibial or patella), and
- No pending component revisions or removals (femoral, bearing, tibial or patella) and
- Absence of Osteolysis in any component (femoral, bearing, tibial or patella) and
- No migration / subsidence of >3mm or >3° in any component (femoral, bearing, tibial or patella)

A patient who meets any of the following criteria at the two-year (\pm 2 months) evaluation will be considered as “failure”:

Patient Failure – defined by the following requirements at the two-year follow-up interval:

- A Knee Score of < 80 , or
- Revisions or removals of any component (femoral, bearing, tibial or patella), or
- Pending revisions or removals of any component (femoral, bearing, tibial or patella), or
- Presence of Osteolysis in any component (femoral, bearing, tibial or patella), or
- Migration / subsidence of 3 mm or $>3^\circ$ in any component (femoral, bearing, tibial or patella).

6.1.4 Surgical Procedure

Standard, accepted surgical procedures for total knee arthroplasty will be utilized. The specific surgical procedure performed at the investigative site is to be documented before study start. All study patients are to be operated on according to the relevant site-specific surgical procedure. Any deviations from this site-specific surgical procedure are to be documented.

After surgery, information is to be collected concerning the surgical details and hospital course of the subject. Information such as length of surgery (skin to skin, tourniquet, instrumentation, and anesthetic times); surgical approach; soft tissue released; ASA Classification; range of motion at discharge; intraoperative complications and prosthesis implanted is recorded.

Appropriate postoperative care will be given and is at the discretion of the physician, as is weight bearing schedule.

Rehabilitation time frame and regimen performed at each investigative site is to be documented before study start. All study patients are to be rehabilitated according to the relevant site-specific rehabilitation procedure. Any significant deviations from this site-specific rehabilitation procedure are to be documented.

6.2. Study Procedures

Patient packs containing all the necessary Case Report Forms for the duration of the study will be supplied to the PI prior to commencing the Study. Samples of the forms are included in the Report Forms section of this protocol.

An Informed Patient consent Form will be completed. Diagnosis may include any confirmatory test as deemed necessary by the surgeon, such as x-ray, CT (computerised tomography) or MRI (magnetic resonance imaging). Standard pre-operative blood and laboratory tests should be conducted.

An Operative Record will be completed to record details of each operative procedure.

6.3. The RSA Procedures

The fixation and stabilization of the tibia components will be assessed using RSA. During the surgical procedure at least three well-scattered tantalum markers are installed (\varnothing 1.0 mm) into the bone around

the tibial component to obtain skeletal landmarks. The tantalum markers are locked inside a rotating cartridge inside a specially designed insertion instrument (Halifax Biomedical, NS, Canada).

At the routine control visits (discharge day, 6 weeks, 3, 6, 12, 24 months and 5 years), the radiographs will be taken and the physical evaluation will be performed.

The RSA data of the prostheses components will be compared in terms of subsidence, linear, and rotational movements and wear. If the prosthesis is stable and fixed the differences will be zero.

The RSA set-up consist of two synchronized roentgen tubes positioned approximately 1.5 meter above two roentgen cassettes (35*43 cm) at a 20° angle to the vertical. Both roentgen tubes simultaneously expose the roentgen film. A carbon fiber calibration box (Medis specials b.v., Leiden, The Netherlands) is used to calibrate the experimental set-up (loaned by Stryker to the hospital for the duration of the study, covered in study contract).

The RSA X-rays of the discharge day (4-7 days postoperative) is used as baseline. Since the tantalum balls are fixed in the bone around the tibial implant, the position of the implant relative to the bone can be calculated. Taking these bone markers as reference points, the spatial translations and rotations of the tibial component during follow-up can be calculated (Kaptein et al., 2006; Valstar et al. 2005). The bone markers need to be well fixated in the bone. Bone markers are defined unstable when they move more than 0.3 mm with respect to the other bone markers. Unstable markers will be excluded from analysis (Garling et al. 2005b).

For the analysis of wear the same principle can be used. Taking the tibial component as a reference, the spatial translations and rotations of the femoral component during follow-up can be calculated. The relative change in proximal – distal direction of the femur with respect to the tibia will be denoted as polyethylene wear.

7. Adverse Events

7.1. Section 10 WMO

In accordance to section 10, subsection 1 of the WMO, the investigator will inform the subjects and the reviewing accredited METC if anything occurs, on the basis of which it appears that the disadvantages of participation may be significantly greater than was foreseen in the research proposal. The study will be suspended pending further review by the accredited METC, except insofar as suspension would jeopardize the subjects' health. The investigator will take care that all subjects are kept informed.

7.2. Definitions

Adverse Event (AE) – “Any untoward medical occurrence in a subject whether it is considered to be device related or not. An adverse event can therefore be any unfavourable and unintended sign, symptom, or disease developed or worsened during the period of observation in the study, whether or not related to the investigational product”

An Adverse Event could be:

- a new illness
- worsening of an illness
- an effect of the study device including the comparator (if any)
- a combination of two or more of these factors

Surgical procedures themselves are not Adverse Events; they are therapeutic measures for conditions that require surgery. The condition for which the surgery is required is an adverse event if it occurs or is detected during the study period. Planned surgery measures permitted by the study and the condition(s) leading to these measures are not adverse events. If the condition(s) was (were) known before the subject enrolled in the study, this (these) should be recorded in the medical history CRF.

Adverse Device Effect (ADE) – “Any untoward or unintended response to a medical device including any event resulting from insufficiencies or inadequacies in the instructions for use or the deployment of the device and any event that is a result of user error”

Serious Adverse Event (SAE) – An adverse event that:

- Led to a death, or
- Led to serious deterioration in the health of the subject that:
 - resulted in a life-threatening illness or injury.
 - resulted in a permanent impairment of a body structure or a body function.
 - required in-patient hospitalization or prolongation of existing hospitalization.
 - resulted in medical or surgical intervention to prevent permanent impairment to body structure or a body function, or
- Led to foetal distress, foetal death or a congenital abnormality or birth defect.

The term “life threatening” in the definition refers to an event in which the subject was at risk of death at the time of the event. It does not refer to an event that hypothetically might have caused death if it were more severe.

Serious Adverse Device Effect (SADE) – “adverse device effect that has resulted in any of the consequences characteristic of a serious adverse event or that might have led to any of these consequences if suitable action had not been taken or intervention had not been made or if circumstances had been less opportune”

